Appendix: Power calculations

Sample size and power calculations were based on a two-sample test of proportions with *power.prop.test* function in *R*.¹² We expect these calculations to be conservative,

because of the precision gained through stratified randomization, covariate adjustment during the analysis, and our pre-specified use of a one-sided hypothesis test.

We estimated 100 participants/arm would provide 80% power to detect at least a 20% absolute increase in viral suppression at 48-weeks from 40% under the standard-of-care. As shown in the following Figure, even with 25% attrition (from 100 to 75 participants/arm) and lower or higher than suppression in the control, these calculations suggest we would be well-powered to detect at least a 22.3% absolute increase in viral suppress.

References

1. van der Laan M, Rose S. *Targeted Learning: Causal Inference for Observational and Experimental Data*. Springer; 2011.
2. Moore KL, van der Laan MJ. Covariate Adjustment in Randomized Trials with Binary Outcomes: Targeted Maximum Likelihood Estimation. *Stat Med*. 2009;28(1):39-64. doi:10.1002/sim.3445

3. Rosenblum M, van der Laan MJ. Simple, Efficient Estimators of Treatment Effects in Randomized Trials Using Generalized Linear Models to Leverage Baseline Variables. *Int J Biostat.* 2010;6(1):Article 13. doi:10.2202/1557-4679.1138
4. van der Laan MJ, Rose S. *Targeted Learning in Data Science*. Springer; 2018.
6. Balzer L, van der Laan MJ, Petersen M, SEARCH Collaboration. Adaptive Pre-specification in Randomized Trials With and Without Pair-Matching. *Stat Med.* 2016;35(10):4528-4545. doi:10.1002/sim.7023
8. Balzer LB, van der Laan M, Ayieko J, et al. Two-Stage TMLE to Reduce Bias and Improve Efficiency in Cluster Randomized Trials. *Biostatistics*. 2021;kxab043. <https://doi.org/10.1093/biostatistics/kxab043>

The intervention is culturally-adapted and skills-based alcohol counseling, consisting of in-person sessions at baseline and every 12 weeks as well as phone-based “booster” calls every 3 weeks between in-person sessions. The intervention is delivered by lay counselors trained by a licensed clinical psychologist, who also provides ongoing supervision and feedback.

The primary objective is to evaluate if the intervention improved viral suppression (<400 copies/mL) among PWH with unhealthy alcohol use after 24 weeks of follow-up. Secondary endpoints, compared between randomized arms at 24-weeks, include alcohol use, as measured by Alcohol Use Disorders Identification Test—

Consumption [AUDIT-C] or phosphatidylethanol [PEth]. Additionally, within the intervention arm, we will report completion of counseling sessions and their fidelity.

2. Population and Characteristics

The population of interest is PWH who are

- Aged 18+ years
- Enrolled or new to HIV care
- At risk of viral non-suppression:
 - HIV RNA>400 copies/mL in the past 12 months
 - Missed visit (>2 weeks and <90 days from scheduled appointment) in the past 6 months
 - Re-engaging in care (>90 days from last scheduled visit) in the past 6 months
 - New HIV diagnosis (not yet on ART or started ART within past 1 month)
- Have unhealthy alcohol use: AUDIT-C over the past 3-months of ≥ 3 for women or ≥ 4 for men

To characterize measurement of this population, we will provide a participant flow diagram (i.e., a CONSORT diagram). Overall and stratified by trial arm and further by sex, we will summarize the baseline characteristics, including sex, age, country, marital status, occupation, education level, literacy level, trial recruitment site (i.e., venue-based or clinic), trial enrollment criteria, baseline ART status and regimen, baseline viral suppression status, and baseline alcohol use via AUDIT-C score and PEth levels. We will categorize age as “younger” if aged 18-30 years. When treated continuously, PEth will be log-10 transformed and values below the limit of quantification (8 ng/mL) set to 0.

3. Endpoint Measurement and Definition

The **primary endpoint** is HIV viral suppression (HIV RNA<400 copies/mL) at 24-weeks. The primary analytic population will consist of all study participants residing in the study region. In other words, the primary analysis will exclude persons who died, withdrew, or moved out of the study region. In the primary analysis, missing endpoint viral loads will be treated as failures (i.e., un suppressed). In pre-specified sensitivity analyses, described below, we will assess the robustness of these analytic choices.

We will also examine the following **secondary endpoints** to capture alcohol use at 24-weeks:

- Composite measure of unhealthy alcohol use: AUDIT-C ≥ 3 for women and ≥ 4 for men or PEth ≥ 50 ng/mL
- AUDIT-C ≥ 3 for women and ≥ 4 for men
- PEth ≥ 50 ng/mL
- Composite measure of unhealthy alcohol use: AUDIT-C ≥ 6 or PEth > 200 ng/mL
- AUDIT-C ≥ 6
- PEth > 200 ng/mL
- Log-10 transformed PEth (treated continuously)

Pending data availability, we will define the primary and secondary endpoints analogously at 48-weeks.

4. Evaluation of the SEARCH Intervention Effect

We will assess the intervention effect with targeted minimum loss-based estimation (TMLE), which improves precision and power by adaptively adjusting for baseline outcome predictors.^{1–5} Here, we will use **TMLE with Adaptive Pre-specification** to flexibly control for baseline covariates, while maintaining Type-I error control and accounting for the randomization scheme.^{6–8} Using 10-fold cross-validation, we will choose the optimal approach for estimating the outcome regression (i.e., the expected outcome given the randomization arm and adjustment covariates) and the known propensity score (i.e., the conditional probability of being randomized to the intervention given the adjustment covariates). Specifically, we will select the combination of estimators (adjustment variables + approach) that minimizes the cross-validated variance estimate.

Our pre-specified, candidate adjustment variables consist of sex, age, country, baseline viral suppression status, baseline PEth (log-10 transformed), baseline AUDIT-C score, and nothing (i.e., unadjusted). Our pre-specified, candidate learners consist of generalized linear models (GLMs) adjusting for a single variable beyond the intervention indicator, stepwise regression, multivariate adaptive regression splines (MARS), MARS after screening based on outcome correlations, and the arm-specific mean outcome.

Primary effect estimates will be for the study sample and on the **ratio scale**:

$1/n \sum_{i=1}^n Y_i(1) \div 1/n \sum_{i=1}^n Y_i(0)$, where $Y_i(1)$ denotes the counterfactual outcome for participant i under the intervention and $Y_i(0)$ denotes the counterfactual outcome for participant i under the control.^{9–11} Secondary comparisons will be on the difference scale.

We will test the **null hypothesis** that the intervention did not improve viral suppression at 24-weeks using a one-sided test at the 5% significance level. We will also report point estimates and 95% confidence intervals for each effect measure and the arm-specific outcomes at baseline and 24-weeks. Standard error estimation will be based on the estimated influence curve, and statistical inference will follow from the Central Limit Theorem (i.e., using the standard normal distribution).¹

Secondary analyses: To assess the robustness of these findings, we will repeat these analyses using the unadjusted effect estimator. We will also repeat these analyses including persons who moved out of the study region, excluding persons with missing endpoints, and using TMLE to adjust for missing endpoints.

Subgroup analyses: We will repeat these analyses within strata defined by country, sex, age group, trial recruitment site, trial enrollment criteria, baseline viral suppression status, and baseline alcohol use: AUDIT-C score 3-5/women or 4-5/men, AUDIT-C score 6-7, AUDIT-C score 8+, PEth<8 ng/mL (undetectable), PEth≥8 ng/mL, PEth<50 ng/mL, PEth≥50 ng/mL, PEth≤200 ng/mL, Peth>200 ng/mL. In subgroups analyses, we will limit the candidate estimation approaches to main terms adjustment for a single covariate or the simple mean and use leave-one-out cross-validation for subgroups with <40 participants. To further understand effect heterogeneity, we may conduct variable importance measures (unadjusted and adjusted) to understand baseline predictors of endline viremia, overall and by arm.

Secondary endpoints compared by arm: We will implement analogous analyses to evaluate the intervention effect on alcohol use. In these analyses, the primary approach will exclude persons with missing measures of alcohol use at 24-weeks. We will again examine the robustness of this approach (i.e., adjust with TMLE for missing measures and include persons who moved out of the study region). When examining the effect on log-10 PEth values, we will use the difference scale.

5. Intervention Fidelity and Implementation

[figure not shown]
Within the intervention arm, we will evaluations of content fidelity and counseling skills at randomly selected in-person sessions. We will also report intervention adherence, as the proportion of participants who completed each counseling session.

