Dynamic Treatment	Mobile Travel Pack intervention 1. Age ≥ 15 years 2. HIV-positive 3. HIV RNA non-suppression (>400 c/mL in the prior 12 months) or missed 2 visits in past 12 months or no VL measured in past 12 months 4. Travel outside the community ≥ 2 times in past 12 months 5. Enrolled or new to care in a study clinic Alcohol intervention 1. Age ≥ 18 years 2. HIV-positive 3. HIV RNA non-suppression (>400 c/mL in the prior 12 months) or missed clinic visits (>2 weeks or ≤ 90 days from last scheduled clinic visit) within past 6 months, or out of care without return to care (>90 days from last scheduled clinic visit) within past 6 months 4. Heavy alcohol use per AUDIT-C tool (scores of ≥ 4 for men, and ≥ 3 for women) 5. Enrolled or new to care in a study clinic Hypertension Linkage and Treatment Interventions	Mobile Travel Pack intervention 1. <15 years of age 2. Participation in another Phase A RCT intervention component Alcohol intervention 1. <18 years of age 2. Participation in another Phase A RCT intervention component 3. No access to mobile phone Hypertension Linkage and Treatment Interventions

	
 1. Age ≥ 25 years (linkage); age ≥ 40 years (treatment) 2. Blood pressure $\geq 140/90$ mmHg on three repeated measurements during community-based hypertension screening for linkage study and $\geq 160/100$ mmHg for the treatment study 3. Resident (by self-report) within catchment area of referral health center 	
 1. <25 years (linkage); age <40 years (treatment) 2. Plan to out-migrate from the catchment area of referral health center within 30 days of screening visit 3. Already engaged in hypertensive care (by self-report) (linkage only) 4. Blood pressure measure of $\geq 180/110$ mmHg during screening and symptoms of hypertensive emergency (linkage only) 5. Pregnant (treatment) 6. Co-morbidities that preclude home monitoring (treatment)
--	--	--

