7.4. Recruitment Process

7.4.1. Phase A

Dynamic Prevention

Outpatient, Antenatal/Family Planning Clinics, Households, and Youth Multi-Sector Interventions:

The study will enroll persons currently active in, or willing to receive care or take part, in 1) outpatient clinics, 2) antenatal/family planning clinics, 3) community households (VHT study) and 4) Youth multi-sector interventions. The youth multisector interventions are tailored to respond to COVID pandemic restrictions. Study leadership will meet with clinic, VHTs, and community leaders to explain the study purpose and goals. In collaboration, study staff will approach consecutive potential participants for participation in the study.

Dynamic Treatment

Heavy alcohol drinkers, mobile populations and those with untreated or severe hypertension: The study will offer Dynamic Treatment intervention components to 2 different populations with unsuppressed viral loads and/or missed visits: 1) mobile populations (travel outside community at least twice in past 12 months), 2) heavy alcohol users (AUDIT-C screening tool scores of ≥4 for men, and ≥3 for women^{70, 71}). For the alcohol trial, staff will recruit from the clinic, and use bar-based mobilization, in which staff will reach out to persons attending bars in study communities and offer referral for multi-disease (e.g., hypertension, diabetes and HIV) screening at each community clinic, with additional screening for trial eligibility among adults identified with HIV. The study will also examine one intervention to promote linkage to hypertension care among persons (age ≥25), regardless of HIV status, who have elevated blood pressure (≥140/90 mmHg) identified during community-based hypertension screening and a second study to evaluate an intensive community-based hypertension treatment intervention vs standard clinic monitoring for those with severe hypertension (≥160/100). Study leadership will meet with clinic directors in the communities to explain the study purpose and goals. In collaboration with study clinic leadership, study staff will approach consecutive potential participants for participation in the study.

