- Retention in care: the proportion of follow-up time where the participant is engaged in clinical care
- ART possession: the proportion of follow-up time where the participant has a full regimen of ART

We will calculate total follow-up time for each participant as the number of days from their trial enrollment to their week-48 viral load measure. (For persons without a week-48 viral load measure, we will use the close the endpoint ascertainment window.) Out-of-care time will start 14 days after a missed visit and end at re-engagement in care.

4. Evaluation of the SEARCH Intervention Effect

We will assess the intervention effect with targeted minimum loss-based estimation (TMLE), which improves precision and power by adaptively adjusting for baseline outcome predictors.^{1–5} Here, we will use **TMLE with Adaptive Pre-specification** to flexibly control for baseline covariates, while maintaining Type-I error control and accounting for the randomization scheme.^{6–8} Using 10-fold cross-validation, we will choose the optimal approach for estimating the outcome regression (i.e., the expected outcome given the randomization arm and adjustment covariates) and the known propensity score (i.e., the conditional probability of being randomized to the intervention given the adjustment covariates). Specifically, we will select the combination of estimators (adjustment variables + approach) that minimizes the cross-validated variance estimate.

Our pre-specified, candidate adjustment variables consist of sex, age, country, being new to care at enrollment, baseline mobility (number of nights away from the community in the past 12 months), baseline viral suppression status, and nothing (i.e., unadjusted). Our pre-specified, candidate learners consist of generalized linear models (GLMs) adjusting for a single variable beyond the intervention indicator, stepwise regression, multivariate adaptive regression splines (MARS), MARS after screening based on outcome correlations, and the arm-specific mean outcome.

Primary effect estimates will be for the study sample and on the **ratio scale**:

$1/n \sum_{i=1}^n Y_i(1) \div 1/n \sum_{i=1}^n Y_i(0)$, where $Y_i(1)$ denotes the counterfactual outcome for participant i under the intervention and $Y_i(0)$ denotes the counterfactual outcome for participant i under the control.^{9–11} Secondary comparisons will be on the difference scale.

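### The alcohol SAP admits new HIV diagnoses by a route that protocol criterion 3 does not list, and leaves that status out of its candidate adjustment variables

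*SAP*

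**What the plan says.** **Protocol, section 7.3.1, alcohol intervention, criterion 3.** The first two routes are "HIV RNA non-suppression (>400 c/mL in the prior 12 months) or missed clinic visits". The third is "out of care without return to care (>90 days from last scheduled clinic visit) within past 6 months". Criterion 5 is a separate requirement: the person must be enrolled in, or new to, care at a study clinic. Section 7.4.1 describes bar-based mobilisation with referral for multi-disease testing, followed by "additional screening for trial eligibility among adults identified with HIV".

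**Alcohol SAP, section 2.** There are four routes. The first three are counterparts of the protocol's, though the third now reads "Re-engaging in care (>90 days from last scheduled visit) in the past 6 months". The fourth is "New HIV diagnosis (not yet on ART or started ART within past 1 month".

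**Alcohol SAP, section 4.** Apart from the unadjusted option, the "candidate adjustment variables consist of sex, age, country, baseline viral suppression status, baseline PEth (log-10 transformed), baseline AUDIT-C score". Enrolment criteria are a baseline descriptor (section 2) and a subgroup factor (section 4), but not a candidate covariate.

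**Mobility SAP, section 4.** This SAP has the same version date and the same suppression threshold of 400 copies/mL. Its candidates begin with "sex, age, country, being new to care at enrollment, baseline mobility".

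**The concern.** The documents do not agree on who qualified for the alcohol trial, and the disagreement bears on prognosis. A person diagnosed last week and about to start ART, and an established patient with viraemia on ART, are both likely to be unsuppressed at baseline. Their chances of suppression at week 24 may differ a good deal. If so, an adjustment that knows only baseline suppression status averages two different groups in one cell and leaves explainable variance in the primary comparison. The SAP already plans to record the variable that would separate them. A subgroup analysis by enrolment criterion does not recover that precision for the overall estimate.

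**Working it through.** **1. The eligibility texts side by side.**

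- *New diagnosis.* The SAP lists it as sufficient on its own; criterion 3 does not mention it. The protocol names comparable routes where it wants them: the mobility criterion in section 7.3.1 accepts having no viral load in the past 12 months, and the Phase B LEAP criterion in section 7.3.2 accepts diagnosis within the last 4 weeks. A newly diagnosed person with no viral load result and no earlier appointment meets the SAP definition but not criterion 3.
- *Missed visit.* The protocol joins its limits with *or* (more than 2 weeks, or 90 days or less), which any missed visit satisfies when read literally. The SAP joins them with *and* (more than 2 weeks and under 90 days), which is a true window.
- *Out of care.* The protocol describes someone who has not returned; the SAP describes someone who is returning.

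**2. The plan's own sample size.** Inputs are 40% against 54%, two-sided 5% and 80% power (protocol section 15.2.1 and the alcohol SAP appendix).

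n = [1.960·√(2·0.47·0.53) + 0.842·√(0.40·0.60 + 0.54·0.46)]² / 0.14² = [1.383 + 0.588]² / 0.0196 ≈ 198.3, so 199 per arm.

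Power at 200 per arm is 80.3%, and the planned one-sided test gives 87.9%. The stated 200 per arm reproduces.

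**3. Does the mix upset it?** Assume new diagnoses are 5–30% of the sample, with control-arm suppression of 50–80%, against 40% in everyone else. The control rate becomes 40.5–52%. Two-sided power for a 14-point gain stays at 80.2–81.5%, and the detectable difference at 13.7–14.0 points. It does not.

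**4. What the indicator could add.** The documents give none of the inputs, so every share and outcome below is assumed, and all new diagnoses are taken as unsuppressed at baseline. R² is the between-group variance divided by p(1−p), first with suppression status alone and then with the new-diagnosis indicator added. Gain in effective sample size = (1 − R²₁)/(1 − R²₂) − 1.

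First row in full:
- p = 0.40·0.85 + 0.50·0.35 + 0.10·0.85 = 0.60, so p(1−p) = 0.24.
- The unsuppressed cell averages (0.175 + 0.085)/0.60 = 0.433.
- R²₁ = [0.40·0.25² + 0.60·0.167²]/0.24 = 0.174.
- R²₂ = [0.40·0.25² + 0.50·0.25² + 0.10·0.25²]/0.24 = 0.260.
- Gain = 0.826/0.740 − 1 = 11.7%.

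| Baseline suppressed | Established unsuppressed | New diagnosis | Overall p | R²₁ | R²₂ | Gain |
|---|---|---|---|---|---|---|
| 40% at 0.85 | 50% at 0.35 | 10% at 0.85 | 0.600 | 0.174 | 0.260 | 11.7% |
| 40% at 0.85 | 50% at 0.35 | 10% at 0.70 | 0.585 | 0.193 | 0.235 | 5.5% |
| 40% at 0.85 | 55% at 0.35 | 5% at 0.85 | 0.575 | 0.206 | 0.253 | 6.3% |
| 40% at 0.85 | 55% at 0.35 | 5% at 0.70 | 0.568 | 0.217 | 0.240 | 3.0% |
| 20% at 0.60 | 70% at 0.30 | 10% at 0.70 | 0.400 | 0.042 | 0.100 | 6.5% |
| 15% at 0.60 | 75% at 0.30 | 10% at 0.85 | 0.400 | 0.029 | 0.141 | 12.9% |

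The first four rows imply overall suppression of 57–60%, above the planning rate. The last two hold it at the planned 40% and give gains of similar size. On 200 per arm, 5.5% is worth 200·0.055 = 11 participants per arm and 11.7% about 23.

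**The case against.** The strongest reply has four parts.

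*The protocol does not shut new diagnoses out.* This stands. A reader might infer from the mismatch that criterion 3 excludes the people whom bar-based recruitment finds. It does not: a newly diagnosed person with a measured viral load above 400 meets the first route, criterion 5 foresees people new to care, and the recruitment text covers all adults identified with HIV, not first diagnoses alone. The accurate statement is that new diagnosis is not listed as a qualifying route.

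*The primary comparison is well defined.* This also stands. The analysis set in alcohol SAP section 3 is all participants residing in the study region, apart from deaths, withdrawals and those who moved away. It does not depend on entry route. The other two wording differences may also matter little in practice: the protocol's separate route for more than 90 days suggests that a window was meant, and an out-of-care person who enrols at a clinic is in effect re-engaging.

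*Candidate covariates are a trial-specific choice.* This is largely fair. Leaving one out does not bias a randomised comparison, and the mobility SAP's new-to-care status need not mean new diagnosis, since it could include people transferring in. But this trial names new diagnosis as an entry route, and its candidate list cannot tell those people from established viraemic patients.

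*The list was fixed in advance.* Enrolment ended in September 2021, so week 24 fell due by about mid-March 2022, before the SAP date of May 19, 2022. The documents do not show whether arm-level outcomes had been seen. That governs how the fix is made.

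**Conclusion.** The point holds as an eligibility mismatch plus a missed gain in precision. It causes no bias and leaves the stated sample size and power intact. A reader might also infer that the 40% planning rate is undermined by new ART starters. It is not, because power for a 14-point difference stays near 80% across the assumed mixes.

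The size of the gain is illustrative: roughly 5–12% in effective sample size if 10% of participants are newly diagnosed and suppress much more often than established unsuppressed patients, and less if the share or contrast is smaller. The calculation ignores the other candidates (age, sex, country, PEth, AUDIT-C), which could absorb part of it. It also needs the selected estimator to use the indicator alongside baseline suppression. Some people up to a month into ART may already be suppressed at baseline, which would shrink the gain further. The downside is small, since Adaptive Pre-specification takes up a candidate only when it lowers the cross-validated variance estimate.

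**What to change.** - **Alcohol SAP, section 4.** If arm-level outcomes have not been seen, add new HIV diagnosis / new to care at enrolment to the candidate adjustment variables. If they have, keep the list as it is and run the extended one as a labelled sensitivity analysis.
- **Protocol 7.3.1 criterion 3 and alcohol SAP section 2.** Reconcile them on three items: whether new diagnosis qualifies by itself, how the missed-visit limits combine, and whether the third route means still out of care or returning. State which definition governed enrolment.
- **Reporting.** Give the number of the 401 who entered only through the new-diagnosis route.

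The cost is one covariate, a wording correction and one extra count. The SAP already plans to summarise enrolment criteria and baseline ART status, so no new data or participants are needed.
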